8.4. Quality Control for Assessments

The quality of the assessments (both baseline and follow-up) will be evaluated by having [name] review a random sample of 10% of all assessments. All assessments will be audio recorded. [name] will review the recordings and discrepancies in the interpretation of participant responses will be discussed and reconciled. The ED staff or the Outcome Assessor may be referred for additional training at [name] discretion if there are many discrepancies.

8.5. Attrition

The following strategies will be implemented to maximize retention. 1) All participants (in both treatment groups) receive diabetes educational materials. 2) All participants receive \$20 and certificates of completion for all outcome assessments. 3) Established relationships with PCPs will convey credibility to participants and sustain research engagement. 4) We will mail birthday cards and a quarterly "Question-and-Answers" newsletter to all participants to maintain positive, personalized contact. 5) We will make reminder calls the day before in-home appointments, and maintain flexibility when scheduling them. 6) We will have a dedicated telephone line for participants to call for study-related questions.

9: DESCRIPTION OF INTERVENTIONS

9.1. PREVENT

PREVENT is a collaborative intervention of PCPs, a DM nurse educator, and CHWs that aims to reduce the need for DM-related ED visits in AAs with DM. To achieve this goal, PREVENT uses culturally tailored strategies to improve DM self-care and access to care. Within 2 weeks of discharge from the ED or hospital, a CHW will begin to deliver six 90-minute in-home treatment sessions (during the 1st four months) and three booster sessions (over the next 8 months). The CHW will: 1) deliver culturally relevant DM self-care education: 2) use DM-specific Behavioral Activation to reinforce DM self-care skills, and 3) facilitate a telehealth visit with the participant's PCP (session 2), and three telehealth visits (sessions 3 and 5, and the 8-month booster session) with a DM nurse educator (Co-I [name], DNP, CDE). At every treatment session, the CHW will complete the Community Health Worker (CHW) Encounter Form. This brief standardized form characterizes CHW treatment activities and participant DM self-care practices. The CHW will upload the Form to the EMR (Epic) for the PCP's review after sessions 1 and 6 (at 4 months). This will enable the PCP to better engage the participant during the telehealth visit (session 2) and in subsequent office visits. For participants who do not have a Jefferson PCP, the CHW will fax the form to the PCP. [name] will supervise the CHW during twice monthly meetings. The CHW will make no treatment recommendations unless previously discussed with [name].

- Session 1: The CHW will establish rapport and describe the collaboration with the PCP and DM nurse educator. She will discuss the reasons for the participant's recent ED visit, experiences with DM self-care (e.g., adherence to medications, diet, glucose monitoring), and barriers (e.g., unhealthy family diet). The CHW will then review culturally relevant educational materials to build DM knowledge and skills according to national standards. The CHW will also rehearse and record a participant's questions (e.g., "Do I skip medications when traveling?") and health beliefs (e.g., "Sometimes I think prescription medications are addictive") to build confidence to discuss these issues with the PCP. The CHW will contact the JeffConnect scheduling office to schedule the PCP telehealth visit (session 2). The CHW will also refer participants (as needed) to social services to ensure that basic needs are met (e.g., safe housing, financial counseling, food security).
- Session 2: This session will begin with the telehealth visit with the PCP (about 20 minutes). The PCP will explain the collaboration with the CHW, and will assess the participant's current health status, answer questions about the recent ED visit, address relevant health beliefs, and review current medications (i.e., purpose, dosing, side effects). If the participant's most recent HbA1c is at target, the PCP reinforces the participant's current DM self-care strategies, and may consider a medication dose reduction. If the HbA1c level is not at target, the PCP will ask about treatment obstacles, and discuss ways to surmount them that are acceptable to the participant (e.g., diet modifications, medication change). After the telehealth visit, the CHW will review the PCP's recommendations with the participant. The CHW might say, "You've been taking metformin only when you thought your glucose was high. Dr. __ advises taking it daily to stay healthy. Let's talk about how metformin works and find a way to take it every day." They may then discuss how to integrate medication-taking into daily routines or a participant's personal values (e.g., trust in God). Taking medications might be linked to the message, "God has given us these medicines to live a

healthy life." At the end of session 2, the CHW and participant will schedule a telehealth visit with the DM nurse educator for session 3.

- Session 3: This session will begin with the telehealth visit with the DM nurse educator, who will discuss the participant's current experiences with DM self-care and will target a participant-selected DM self-care goal. Using DM-Specific Behavioral Activation, the DM nurse educator, CHW, and participant will devise an Action Plan for that activity. For diet, an Action Plan might target healthy food choices, food portions, timing meals, and discussing dietary needs with family. The CHW will provide skills training as needed (e.g., plate method to organize meals, using a glucometer). The Action Plan goal might be to reduce soft drink consumption or eat 3 vegetables daily. The Action Plan steps specify the "how, when, and where" of the plan, and are observable, quantifiable. integrated into daily routines, and attainable (to provide positive reinforcement). An Action Plan for exercise (e.g., "walk with a friend") might be: 1) call a friend; 2) pick a date/time; and 3) use a pedometer (supplied) to track distance walked. These steps are recorded on a large print calendar to provide cues to action. Over the next week, the participant will record the number of times the Action Plan is completed, and will rate their sense of accomplishment (to enhance reward salience). The CHW will also anticipate negative perceptions (e.g., "I can't do this" or "This will never work") and encourage the participant to "make room" for these thoughts while still following the Action Plan (i.e., "Follow the plan instead of the feeling").
- Sessions 4-6: The CHW and participant will review previous Action Plans. The CHW will reinforce attained DM self-care goals, help set new ones, and facilitate access to upcoming PCP clinic visits [e.g., discuss barriers (e.g., transportation) and health beliefs (e.g., "check-ups aren't really necessary."); rehearse questions for PCP; and mark upcoming appointments on a calendar]. If a participant has an ED visit and/or hospitalization during treatment, [name] and the CHW will identify modifiable predisposing or precipitating factors, and develop an Action Plan to address them. Session 5 will include the 2nd telehealth visit with the DM nurse educator to answer questions, identify treatment barriers, and set new DM self-care goals. After session 6, the CHW will upload the current CHW Encounter Form for the PCP's review.
- Booster Sessions (Months 6, 8, and 10): These 3 booster sessions will sustain treatment engagement and reinforce DM self-care. A telehealth visit with the DM nurse educator will occur at month 8. During the booster sessions, the CHW and participant will discuss current medical care and upcoming PCP visits, and review and modify previous Action Plans to accommodate changes in health or social circumstances.

9.2. EUC

EUC is comprised of usual primary care that is enhanced with individualized DM self-care education. EUC is a credible intervention that matches PREVENT in treatment intensity, educational materials, delivery characteristics, and referral to community resources as needed, but does not include DM-specific Behavioral Activation or telehealth. The EUC control: 1) ensures that all participants will receive DM self-care education; 2) reduces risk of unmasking (i.e., all participants will have in-home visits; and 3) reduces attrition (all participants will have attention to their DM). Interventions like EUC accord with the American Association of Diabetes Educators' position statement on CHWs. In EUC, the CHWs will deliver an accurate, culturally relevant understanding of DM, and use supportive techniques (e.g., encourage personal expression, convey empathy) to create an accepting treatment

environment. The CHW EUC interventionist will document: 1) the number/duration of sessions; 2) the extent/quality of participant adherence; 3) treatment satisfaction; and 4) friend/family involvement.

10: DATA AND SAFETY MONITORING PLAN

10.1 Potential Risks and Benefits for Participants

Potential Risks:

The potential risks to study participants form the study assessments include:

- (1) Breaches in confidentiality
- (2) Psychological discomfort associated with answering questions about health beliefs, quality of life, function, adherence to diabetes self-management behaviors, and depression
- (3) Inconvenience or fatigue associated with the baseline and follow-up assessments

HbA1c will be measured with a fingerstick. Although highly unlikely, there is a remote possibility that there will be pain, brushing, or infection at the site of the finger stick.

Potential Benefits:

The potential benefits to all study participants include:

- (1) Receipt of culturally relevant education on diabetes and depression
- (2) Evaluation of cognitive functioning
- (3) Detection of unstable medical or psychiatric condition, diagnosis of dementia, or unsafe living situation and subsequent action to be undertaken by study staff (e.g., referral to primary care physicians, local memory clinics, acute medical or psychiatric services, social services, and crisis intervention)
- (4) Sense of altruism from participating in a study that may lead to effective ways to manage diabetes

10.2 Adverse Event and Serious Adverse Event Collection and Reporting

10.2.1. Alerts and Serious Adverse Events

An adverse event (AE) is any unfavorable and unintended diagnosis, symptom, sign (including an abnormal laboratory finding), syndrome or disease which either occurs during the study, having been absent at baseline, or if present at baseline, appears to worsen. Adverse events will be reported regardless of their relationship to the study intervention.

A serious adverse event (SAE) is any adverse event that results in death, is life threatening, or places the participant at immediate risk of death, requires or prolongs hospitalization, causes persistent or significant disability or incapacity, or any other condition which the PI or DSMB judges to represent significant hazards.

All AEs and SAEs will be reported regardless of their relationship to the study intervention.

Solicited AEs and SAEs will be detected at the follow-up assessments to occur at 6 and 12 months. The Outcome Assessor will use a structured questionnaire to inquire about hospitalizations, emergency room visits, surgeries, and physician visits. The Outcome Assessor will also assess depressive symptoms and suicidal ideation. In addition, every 6 months staff will review participants' medical charts to identify new medical diagnoses, emergency department visits, and hospitalizations.

Unsolicited AEs and SAEs will be detected when participants spontaneously report a medical event during a phone call or a PREVENT or EUC treatment session.

10.2.2. Alerts

In providing oversight to human subject safety, an Alert is distinguished from an AE and an SAE. An Alert is considered to be a dangerous situation discovered to exist by a member of the research team that is not related to the conduct of the research study. Alerts are not specific to or consequences of the study but represent situations that may be encountered in any interaction with a participant. Examples of Alerts include hazardous home conditions (e.g., no heat, no electricity, insect infestation), inadequate food supply, potential abuse/neglect, or inability to access health care/medications. The PI will train study staff on the recognition and handling of common alerts. Study staff will be required to report all alerts to the Project Director immediately, who will maintain a log of all reports, the plan of action, and the outcome of the plan. Staff will be given a Resource List that contains a description of and contact information for local agencies that are equipped to provide assistance for Alert situations (e.g., Area Agencies on Aging). The provision and outcome of all referrals will be tracked.

10.2.3. Reporting of AEs, SAEs, and Alerts

All AEs, SAEs, and Alerts will be reported to the IRB. The Study Coordinator will prepare the appropriate IRB documentation, and will forward it to the PI. The PI will review the event, and will rate its severity and determine whether it is related to study participation.

All AEs, SAEs, and Alerts will be reported to the DSMB. All will be classified along the following dimensions: (1) severity; (2) whether it was expected or not; and (3) the extent to which it was related to study participation. The PI will rate the seriousness of the event. A report detailing AEs and Alerts will be submitted to the DSMB at designated intervals (e.g., quarterly) as determined by the DSMB during study start-up.

For events that are judged by the PI to be ongoing, the Study Coordinator will make weekly calls to the participant to collect updated data regarding the event. This process will continue until the PI determines that the event is terminated, at which time a follow-up report will be submitted to the IRB and the DSMB.

10.3. Protection Against Study Risks

10.3.1. Protection Against Risks

We will minimize the risk of hypoglycemia by having primary care physicians (PCPs) carefully review participants' current medication regimens, previous HbA1c levels, and risk of hypoglycemia based on previous hypoglycemic episodes and other risks. For enrolled participants, PCPs will adjust hypoglycemic medications (e.g., reduce dose of a sulfonylurea) if they are concerned that increased adherence may cause hypoglycemia. We will encourage participants to regularly check their blood glucose, particularly if they feel light-headed, shaky, or weak.

We will minimize the risk of discomfort during assessments and treatment by selecting staff based on their interpersonal sensitivity and capacity to communicate with older persons. We will train staff to recognize signs of distress and fatigue and will terminate testing or treatment if indicated. The assessment instruments have been well-tolerated in our previous studies with African Americans.

We also train the staff to recognize medical events (e.g., hypoglycemia) that warrant intervention at all stages of this project, including screening and follow-up assessments. Since screening will occur in the Emergency Department, medical assistance will be available if needed. For in-home assessments and treatment visits, staff will be instructed to call the PI if they encounter a situation that may warrant medical attention. Events of concern include suicidal ideation, hypoglycemia, HbA1c levels ≥ 10.0% and participant-reported recent blood glucose level over 300, foot ulcers, and any other symptomatic medical condition that the participant reports or that staff observe. For psychiatric emergencies (e.g., suicidal ideation), staff will call PI [name], a geriatric psychiatrist. Conditions of special interest include:

a. Suicidal Ideation: To detect suicidal ideation, staff will administer the Patient Health Questionnaire-9, which includes a question asking if the participant has thoughts that he/she would be better off dead, or has had thoughts of hurting him/herself. If a participant endorses suicidal ideation, staff will be trained to follow a protocol for at-risk participants.

For individuals who express suicidal ideation at any time during the study, staff will administer the Columbia Suicide Severity Rating Scale, which distinguishes passive from active suicidal ideation, and includes specific questions on level of intention and controllability, and any specific plans of self-harm. Staff members are instructed that participants who state that they have considered suicide, have a plan, and either intend to harm themselves, or may not be able to prevent themselves from self-harm, represent an immediate risk. If it is detected during the in-home assessments or intervention visits, staff will be advised to contact [name] ASAP, who will then talk with the participant to assess the risk, and determine an appropriate course of action. If the participant does not pose an immediate risk, staff will nevertheless notify [name], who will contact the participant within 24 hours to assess the participant and devise a plan of treatment, or recommend a course of action to study staff.

b. Cognitive Impairment: If incident cognitive impairment and/or functional disability (e.g. difficulty managing medications) is detected, staff will contact [name] to identify diagnostic/treatment steps to ensure adequate evaluation, treatment, and safety.

c. Abuse or Neglect: If staff determines that a participant is a victim of abuse or neglect, after discussion with [name], we will file a report with the appropriate agency that services the area in which the participant lives.

All research procedures are designed to ensure participants' confidentiality. We will assign each participant a unique identification number; this ID number will be the only identifying information on data forms. Participants' names will not appear on interview forms. A list linking ID numbers to names will be kept in a password-protected computer file accessible only to project staff. Audiotapes of interview and/or intervention sessions to monitor treatment fidelity will be identified by the unique identifier and will not contain participants' names or any identifying information.

Because this study is testing a low risk behavioral/educational intervention, there are no circumstances in which participants will be involuntary discontinued from the study.

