8.2. Preservation of masking

This is a single-masked trial. The Outcome Assessor will be masked to treatment assignment. The PI, participants, the Project Director, the Study Coordinator, the CHW interventionists, the diabetes nurse educator, and PCPs treating participants randomized to PREVENT will be unmasked. Since this study is testing a behavioral intervention and there are no anticipated risks associated with study participation, there are no circumstances in which there will be unmasking based on untoward medical events.

An unavoidable aspect of behavioral intervention research is that participants are aware of their treatment assignments. Several measures will be undertaken to preserve the integrity of masking. First, the Outcome Assessor, who assesses all outcomes, will have no knowledge regarding treatment assignment. Masked staff will not have access to any data files or charts that contain information on treatment assignment. Hard copies of data will be stored in a locked, secure file room at Jefferson. Electronic copies will be stored on an encrypted, password protected server. Second. prior to performing any assessment, the Outcome Assessor will emphasize to all participants the importance of not revealing their treatment assignment. They will be instructed to call the Study Coordinator should they have any questions about this. Third, the Outcome Assessor and the CHW interventionists will be instructed to never discuss any of the participants with each other, either generally or specifically. Fourth, for quality control purposes, after each follow up assessment, the Outcome Assessor will be asked to indicate his/her best guess of which study group the participant is in, as well as his/her reasons for this estimate. If at any time the Outcome Assessor learns of a participant's treatment group, he/she will notify the Study Coordinator immediately, and she will document it so that statistical analyses can be adjusted accordingly. The biostatistician will specifically examine whether unmasking leads to the introduction of treatment-related biases in all reporting of study results. In addition, a research assistant who works in the PI's lab and is employed by the Department of Neurology at Jefferson, will be trained to conduct the follow-up assessments. If a participant's treatment assignment is revealed to the Outcome Assessor, the research assistant will conduct that particular participant's subsequent follow-up assessments.

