APPENDIX 4: GENERAL INSTRUCTIONS FOR THE OUTCOME ASSESSOR

- 1) Please update the Contact Information Form at the 6 and 12 month assessments.
- 2) Unmasking:
 - Please ask the participant to NOT tell you what group they are in.
 - If the participant or any staff member discloses a participant's treatment assignment, please email [name] and [name] ASAP.
- 3) Missing data should be coded as follows:
 - Not Applicable = 9999
 - Refused = 7777
 - Missing due to impaired vision = 8888
 - Reason for missing data unknown 5555

4) Not Applicable (NA):

- NA is to only be used in 2 circumstances:
 - The question does not apply to the participant.
 - The participant is physically unable to respond to a cognitive question/task.
- Low literacy is not a reason for using NA. For example, if a participant is not able to read the
 words on the LAD, the response for each word should be "incorrect". Being wheelchair bound
 is also not a reason for using "NA" on questions regarding walking. These questions should be
 coded to reflect the fact that the participant is not able to do the activities.
- For the Diabetes Self Care Inventory, if a participant indicates that they never have low blood sugar, their response should be "never do it". This scenario also applies to question 6 (carry quick acting sugar for lows).
- For the questions on hypoglycemia, if the participant responds "No" to the first question (have you had a hypoglycemic episode), the response to the remainder of the questions in this section should be NA. Otherwise, all questions must have a response other than NA.
- 5) Part 2 of the baseline assessment:
 - Our goal is for all Part 2s to be completed within 2 weeks of Part 1.
 - This is very important to maintain participant interest in the study and to insure integrity of study data.

6) A1c results:

- Take a photo of the result with your Jefferson-issued iPhone and email to [name], [name], and [name].
- Please make sure the proper study ID is on the image.
- Enter the result in REDCap.

• [name] will verify the result entered in REDCap against the image.

7) Medication lists:

- At Part 1 of the baseline assessment, the ED staff will obtain a list of medications from EMR.
- At 6 and 12 months, staff will obtain medication lists from EMR.
- At the in-home assessments (Part 2 of baseline, 6, and 12 months), the Outcome Assessor will obtain self-reported medications.

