APPENDIX 5: GENERAL INSTRUCTIONS FOR INTERVENTIONISTS

- 1) To schedule telehealth visits with the PCPs, call [name]. These visits will be conducted via MyChart. Note that this does not apply if the participant does not have a Jefferson PCP.
- 2) To schedule telehealth visits with [name], contact her directly.
- 3) The audio recorder should not be on during the telehealth visits.
- 4) If you give the participant a mental health referral, please inform the PCP ASAP, and let them know where you sent the participant for care.
- 5) Please turn in all paperwork from the initial 6 sessions to the Study Coordinator within 2 weeks of the 6th session. Please enter the paperwork in REDCap and turn in any hard copies. Please turn in paperwork from the booster sessions within 2 weeks from each booster session. Tapes should be posted within 1 business day of the session being completed. The Study Coordinator will document that the paperwork was handed in, and it will then be scanned (and stored on the shared drive).

[figure not shown]

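### Hypoglycemia is a harm the plan foresees, but its risk statements conflict and no planned summary by arm would show whether it rose

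*Combined protocol and SAP*

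**What the plan says.** **Risk statements.** Section 10.3.1 opens with hypoglycemia: "We will minimize the risk of hypoglycemia by having primary care physicians (PCPs) carefully review participants' current medication regimens". It then ties the risk to what the intervention tries to achieve: "PCPs will adjust hypoglycemic medications (e.g., reduce dose of a sulfonylurea) if they are concerned that increased adherence may cause hypoglycemia". Section 8.2, explaining why no emergency unmasking is foreseen, states that "there are no anticipated risks associated with study participation". Section 10.4 expects no special risks from PREVENT. The list in section 10.1 is introduced by "The potential risks to study participants form the study assessments include" and adds only the fingerstick.

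**Safety collection.** Section 10.2.1 says of the follow-up visits: "The Outcome Assessor will use a structured questionnaire to inquire about hospitalizations, emergency room visits, surgeries, and physician visits". It adds depressive symptoms, suicidal ideation and a six-monthly chart review. Every AE and SAE is reportable whatever its presumed cause. Section 10.2.3 sends all of them to the IRB and the DSMB, graded for severity, expectedness and relatedness. Section 10.3.1 also has staff call the PI about hypoglycemia.

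**Questions on episodes.** Appendix 4, item 4, shows that the assessor's instrument contains a hypoglycemia block ("For the questions on hypoglycemia, if the participant responds" begins its coding rule). Section 6.2 and Table 5 do not mention the block.

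**Analysis.** Table 3 places hypoglycemia and hyperglycemia codes under one heading, and both count toward the primary outcome. Section 10.5.2 lists AEs, SAEs and Alerts generically. Section 13.1 plans no hypoglycemia analysis.

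**The concern.** PREVENT aims to improve self-care, including medication taking. The plan itself says that better adherence may produce hypoglycemia, so this is the medical harm that it links to the intervention. A reader of the results will want to know whether it was more frequent under PREVENT than under EUC.

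The primary count cannot answer that. A fall in hyperglycemic or other diabetes-related visits and a rise in hypoglycemic visits offset each other within one total. Reporting individual events to the DSMB does not compare the arms either. Episodes managed at home are asked about, but the plan does not say what becomes of the answers. The trial could report benefit on acute care without having summarized the harm that it foresaw.

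**Working it through.** The plan states no hypoglycemia rate and no power calculation, so there is no figure to reproduce. The check has three parts.

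**1. Tracing hypoglycemia through the plan**

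| Step | What is provided | What is missing |
|---|---|---|
| Risk statement | 10.3.1 names it | 8.2, 10.1 and 10.4 do not reflect it |
| Acute-care episodes | ED visits and hospitalizations solicited and chart-reviewed as AEs/SAEs (10.2.1) | Not identified as hypoglycemia in any planned summary |
| Other episodes | Appendix 4 questions; spontaneous reports; call to the PI (10.3.1) | No route from the questions to AE reporting; visits at which they are asked not stated |
| Special-interest conditions | 10.3.1 lists suicidal ideation, cognitive impairment, and abuse or neglect | Hypoglycemia not listed |
| DSMB | Generic AE, SAE and Alert content (10.5.2); blinded presentation in open sessions or reports (10.6.2) | No hypoglycemia line and no stated split by arm |
| Final analysis | Pooled count (Table 3, section 13.1) | No hypoglycemia estimate |

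By contrast, the suicidal-ideation item of the PHQ-9 has an explicit onward route in Appendix 4, item 8.

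**2. Offsetting within the primary count**

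Let *s* be the hypoglycemia share of EUC events and *h* the rate ratio for hypoglycemic visits; both are assumed. All other events are assumed to halve, a ratio borrowed from the primary hypothesis in section 13.1.1.

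Pooled rate ratio = 0.5 × (1 − s) + h × s

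- h = 2, s = 0.10: 0.5 × 0.90 + 2 × 0.10 = 0.45 + 0.20 = 0.65
- h = 2, s = 0.20: 0.5 × 0.80 + 2 × 0.20 = 0.40 + 0.40 = 0.80
- h = 2, s from 0.05 to 0.30: 0.575 to 0.95
- h = 1.5, s from 0.05 to 0.30: 0.55 to 0.80
- h = 3, s = 0.05, 0.10, 0.20, 0.30: 0.625, 0.75, 1.00, 1.25

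With h = 2 the ratio reaches 1 when 0.5 + 1.5s = 1, that is s = 1/3. Below that share, a doubling of hypoglycemic visits coexists with an apparent benefit.

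**3. What a table by arm could show**

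Power to detect a doubling in the proportion of participants affected, two-sided 0.05 (assumed level and rates):

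| EUC vs PREVENT | 78 per arm (randomized) | 115 per arm (planned) | n per arm for 80% |
|---|---|---|---|
| 3% vs 6% | 14.5% | 19.4% | 749 |
| 5% vs 10% | 21.8% | 30.1% | 435 |
| 10% vs 20% | 41.6% | 56.6% | 199 |
| 15% vs 30% | 61.3% | 78.1% | 121 |

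Such a table would describe the arms. It would not be a powered test and could not exclude a doubling.

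**The case against.** The strongest reply is that the safety net is wider than the risk list suggests. A reader might infer that hypoglycemic visits are counted only as efficacy events and that an increase would go unseen. The documents do not support that. Section 10.2.1 collects ED visits and hospitalizations as AEs/SAEs by interview and chart review, 10.2.3 sends them to the DSMB, and the AE definition is broad enough for an episode treated at home. The DSMB may also ask for anything further (10.5.2). All of this stands. It secures reporting of individual events, but it still does not plan a comparison by arm.

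Four other tempting readings also go too far:

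- **PCP review is the only safeguard.** Section 10.3.1 adds glucose-check advice and staff training, and 7.6 trains both arms' interventionists in handling low glucose. For PCPs outside Jefferson, the Encounter Form is faxed (9.1).
- **Hypoglycemia would be classed as unexpected.** Nothing ties expectedness in 10.2.3 to the list in 10.1, which is introduced as covering the assessments. The classification is unsettled rather than wrong.
- **Hypoglycemia is the only treatment-related harm named.** Section 10.3.1 also says "We will minimize the risk of discomfort during assessments and treatment by selecting staff". Hypoglycemia is the medical harm linked to the intervention.
- **Pooling in Table 3 destroys information.** Diagnostic codes and presenting symptoms are recorded for each event (6.2), so separation remains possible.

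It is also fair to say that the hypoglycemia share is invented for illustration, that any comparison would be imprecise, and that recruitment has ended. The last point limits changes to conduct more than changes to reporting; the documents do not give the follow-up status. The consent form and the questionnaires are not available here, so nothing is inferred from them.

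**Conclusion.** The point holds in a limited form. The plan names hypoglycemia from increased adherence as a risk, contradicts this elsewhere, asks about episodes without saying how the answers are used, and plans no hypoglycemia summary by arm for the DSMB or the final report. An apparent benefit on the primary count could coexist with an increase that no planned summary would show.

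The size depends on assumptions. If other events halve and hypoglycemic visits double, the pooled rate ratio is 0.65 at a 10% hypoglycemia share of EUC events and 0.80 at 20%. The documents give neither the share nor the hypoglycemia rate ratio, and nothing here suggests that hypoglycemia did increase. The gap is in planned presentation and in the route for the answers; collection of acute-care events as safety data is not in doubt. The change is worth making because it costs little and decides what the trial can report about a harm that it foresaw.

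**What to change.** 1. Reconcile sections 8.2, 10.1 and 10.4 with 10.3.1, and list hypoglycemia in 10.1, so that expectedness under 10.2.3 is judged consistently.
2. In 10.2.1, treat positive answers to the existing hypoglycemia questions as solicited AEs, at whichever follow-up visits they are asked. State those visits, and add the questions to section 6.2 and Table 5.
3. In the final report and in closed-session DSMB material, tabulate by arm (a) self-reported episodes and (b) ED and hospital events under hypoglycemia codes, separately from hyperglycemia. Give confidence intervals and label the table descriptive. Fix the code list beforehand, including how events that enter through the E08-E13 footnote of Table 3 are sorted. Leave the primary count unchanged.
4. Reconcile the sections on which participants receive the stated PCP medication review. Section 10.3.1 refers to enrolled participants generally; 9.1 places the PCP telehealth visit in PREVENT session 2; 9.2 gives EUC no telehealth. Appendix 1 links MyChart to PCP telehealth in PREVENT with or without a Jefferson PCP, while Appendix 5 says of scheduling those visits: "Note that this does not apply if the participant does not have a Jefferson PCP". No clinical rule is proposed here.

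The cost is rewording, more AE forms to process, and a small set of tables from data already collected. The tables will have low power (about 22% for 5% vs 10% at 78 per arm, assumed rates), so a null comparison must not be read as evidence of safety.
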